5.9 Key exclusion criteria

Patients will be excluded from the study if they:

- 1) Have a documented allergy to flu vaccine
- 2) Have a flu vaccine exclusion modifier in Health Maintenance
- 3) Have opted out of research according to individual site guidelines and policies
- 4) Have no phone number (home or mobile) listed in their chart

6. Subject recruitment

Information on PCPs and their patients at Penn Medicine, UW Medicine, and Lancaster General Health will be obtained from the electronic health record using Clarity, an Epic reporting database.

7. Subject compensation

No compensation will be offered in this study.

8. Study procedures

8.1 Consent

A waiver of informed consent is requested and has been approved for this project in accordance with other, similar health system interventions and based on our prior meetings with the Penn IRB. This is a low-risk study conducted in partnership with clinical operations, and it is not feasible to consent every patient and clinician for a project of this scope, where the emphasis is on low cost, scalable interventions. Additionally, clinicians are being nudged towards evidence-based care that is standard of care within the three health systems for this project and based on the United States Preventive Services Task Force evidence-based guidelines. Patients and clinicians are not being forced into receiving a flu vaccine but, instead, this project is evaluating novel nudge interventions to help make it easier for clinicians and patients, especially those who are high risk, to deliver or receive evidence-based care. Patients and clinicians retain autonomy to not proceed with a vaccine for any given visit.

8.2 Procedures

--Interventions--

All patients in the intervention arm with a new or return, non-urgent/sick visit with a PCP will be identified 4 days before their scheduled appointment and sent an endowed text message 72 hours prior to their appointment (standard messaging). The message will inform the patient that a flu shot has been reserved for them at their upcoming appointment. A second nudge will be delivered at 24 hours prior to the scheduled appointment reminding them of their upcoming appointment and encouraging the patient to ask their PCP about receiving the flu vaccine.

In addition to the standard endowed text message nudge, high-risk patients randomized to receive the high-risk intensification nudge will also receive a bidirectional text intervention in the 72-hours prior to their visit. This intervention will query the patient about common questions or concerns about receiving the flu vaccine. If the patient responds, it will provide additional educational materials based on the patient's specific concern(s). If the intervention is unable to satisfactorily address a patient's questions or concerns, a final text will be sent 15 minutes prior to the eligible visit to remind the patient to discuss their unaddressed concerns with their PCP.

The first clinician nudge uses a default, pended order for the flu vaccine that will be visible to the provider during the visit encounter. Clinical staff will have the option of signing the order or dismissing it if they deem it inappropriate for a given patient.

The second clinician nudge is monthly peer comparison feedback that will be sent as an email facilitated by mail merge via Outlook or other bulk email platform per site preference. Clinicians will be told what percent of their eligible patients received the flu vaccine and how that compares to other peer clinicians in the intervention. If the completion rate is below the median rate, the clinician will receive feedback comparing their rate to the median. If it is above the median but below the 90th percentile, the clinician will receive feedback comparing their rate to the 90th percentile. If the clinician's rate is above the 90th percentile (defined as a top performer), they will receive an email informing them that they are a high performer. Residents and fellows will be excluded from the peer comparison analysis and messaging.

--Data--

Data on PCPs and their patients at Penn Medicine, UW Medicine, and Lancaster General Health will be obtained from Clarity (Epic's data reporting database). Clinician data includes gender and type of medical degree. Patient information includes demographic information, information about comorbid conditions (including diabetes, hypertension, and chronic kidney disease, and comorbid conditions needed to calculate the Charlson Comorbidity Index), contraindications for flu vaccine, appointment data, and flu vaccination administration.

--Randomization—

Primary care clinic level randomization will occur electronically. We will randomize clinics 2:1 to the nudge arm or control arm using covariate-constrained randomization.¹⁰ Covariate-constrained randomization first enumerates a large number (e.g., 50,000) of possible intervention allocations. Then, a measure of covariate balance is computed with respect to a set of pre-specified covariates for each possible allocation. Finally, from a subset of possible allocations that achieve adequate covariate balance, one is randomly chosen as the final allocation of interventions for the study. We will implement a version of covariate-constrained randomization that stratifies by health system (Penn and UW) and balances the distribution of clinic size and panel risk across arms. The randomization procedure will be implemented in R¹¹ using the cvcrand package.¹² For the replication trial at Lancaster General Health, we will implement covariate-constrained randomization using the cvcrand package to balance the distribution of clinic size and panel risk across arms.

Within the high-risk patient subgroups, stratifying by intervention clinics, patients will be randomized 1:1 in Way to Health using permuted block randomization using random block sizes of 2, 4, and 6 to receive the additional intensification bidirectional text messaging nudge or standard messaging.

9. Analysis plan

Prior to analyses, we will produce data summaries to assess data quality, data distribution, and randomization success. To ensure even comparison across practices and arms, we will classify eligible patients at 4 days before a scheduled appointment for a new or return visit with their primary care clinician as being enrolled in the study. The primary analysis will be performed using an intention-to-treat approach. Specifically, patients who

do not show up to the first scheduled clinician visit will be considered enrolled and included in the primary analysis.

--Power Calculations--

For the following power calculations, we used an adjusted Type I error of 0.025 to account for two comparisons: 1) clinic-level nudges versus usual care, and 2) intensification for high-risk patients versus no intensification within practices where clinic-level nudges are provided. Based on retrospective data from our health systems, we will have 85% power to detect a 7-percentage point difference in the flu vaccine completion rate for comparison #1. This calculation assumed N=48 participating clinics across the two sites, an average cluster size of n=1385 patients, and an intracluster correlation (ICC) of 0.02. For comparison #2, we will have at least 99% power to detect a 2-percentage point difference even if the rate of vaccination in the high-risk group is 50%, the most conservative rate with respect to power. This calculation assumed 1:1 individual-level randomization of n=1000 high-risk patients within each of N=32 clinics that will be randomized to receive clinic-level nudges. These power calculations used combined retrospective data from Penn and UW to estimate the average number of patients per clinic and the number of high-risk patients who will be randomized. We expect to have greater power for both comparisons at the replication site which comprises more clinics and patients.

--Statistical Analysis--

The primary analysis will fit generalized estimating equations (GEE) with a binary outcome indicating whether a flu vaccine was received during the PCP visit (primary). Following the intention-to-treat framework, patients who do not complete their first scheduled visit will contribute a primary outcome of zero, indicating a flu vaccine was not received during the PCP visit. We will also perform analyses based on a binary outcome that indicates whether a flu vaccine was received 3 months after the first scheduled visit, regardless of whether the visit was completed (secondary). An exchangeable working correlation will be specified at the clinic level for comparison #1 (evaluation of clinic-level nudges) and robust standard errors will be provided, clustered at the clinic level. An independence working correlation and robust standard errors without clustering will be used for comparison #2 (evaluation of individual-level nudges). In sensitivity analyses we will explore alternative specifications for the working correlation structure to examine robustness of parameter estimates and inference. In additional sensitivity analyses, we will censor patients with a PCP visit late in the intervention period (February/March) who are unlikely to complete a flu vaccine beyond March and will therefore not have a full 3 months to obtain a vaccine and examine completion rates among these patients.

We will examine effects of the interventions on overall rates of ordering. We will compare rates of ordering between the three intervention arms: 1) Control, 2) Clinic-level nudges only, and 3) Clinic-level nudges with intensification for high risk. We will fit a GEE with binary outcome indicating whether an order was signed or not. We will fit the model using the weighted and replicated approach¹³ to account for the fact that low-risk patients seen in the clinics that received nudges are consistent with both intervention arms 2) and 3). We will include terms for the main effects of clinic-level and individual-level nudges as well as their interaction. We will test the appropriate linear combinations of the parameters that correspond to pairwise differences between each of the three intervention arms. An independence working correlation with robust standard errors will be

used to account for uncertainty in the weight distribution due to variability in the empirical proportion of high- versus low-risk patients.

We will account for the clinic-level covariate-constrained randomization by including health system, clinic size, and panel risk as covariates in the models for the effect of clinic-level nudges. In models for estimating the effect of intensification on high-risk patients, we will control for differences across health system by including clinic fixed effects which will also account for the stratified randomization.

We will perform exploratory subgroup analyses by risk group as it is defined for the individual randomization. For the low-risk strata, this will allow us to study the effect of the clinic-level nudges versus usual care amongst low-risk patients. For the high-risk strata, we will fit models that include each category used to define high risk (e.g., sex, race, previous year vaccination) as well as their interaction with treatment arm to determine which high-risk subgroups experienced the greatest benefits of the clinic- and individual-level nudges. We will also include a visit-level analysis with clustering by patient as an exploratory analysis.

Investigators and analysts will be blinded to study arm assignment during the intervention and analysis phases. The statistician is responsible for clinic-level randomization, but subsequently will be blinded to study arm assignment for the remainder of the intervention phase and analysis phase. Project staff (site PIs, project director, project manager, and study coordinators) will be unblinded during the intervention and analysis phases to complete daily study activities and prepare the blinded analysis files. Unblinding for investigators, statisticians, and analysts will be completed by the project staff and occur at the end of study analysis once all of the outcomes have been ascertained.

10. Investigators

[name], MBA, MSHP is a Multiple Principal Investigator (MPI) and an Associate Professor of Medicine and Health Policy at the Perelman School of Medicine (PSOM). He has prior experience leading clinical trials to deploy interventions that leverage behavioral economics and technology to improve population health outcomes.

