For clinicians within the intervention arm, a flu vaccine order will be pended on their behalf prior to the PCP visit. This will frame vaccination as the default choice (opt-out rather than opt-in) while reducing clinician/care team effort by removing the need to individually order each vaccine. The unsigned order will be visible to the provider during the visit and they will maintain the option to sign or cancel the order.

In addition to the pended order, eligible clinicians within the intervention arm will receive a monthly peer-comparison feedback message describing their flu vaccine completion rate, relative to that of their peers. We will deliver this feedback via email and vary feedback based on clinicians' vaccine completion rates. PCPs whose completion rates are below the median rate will receive feedback relative to the median rate; PCPs whose completion rates are between the median and the 90th percentile will receive feedback relative to the 90th percentile, and those above the 90th percentile will not receive peer comparisons but will get positive feedback that they are high performers. This tiered approach has previously been shown to motivate clinician behavior and prevent regression to the mean among high performers. Figure 1 provides an overview of the study design. We will use this design to replicate our findings at a third site, Lancaster General Health.

[figure not shown]

Figure 1. Overview of study design

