BE IMMUNE: Behavioral Economics to IMprove and Motivate vaccination Using Nudges through the EHR

University of Pennsylvania

[name]

[name]

[name]

NCT#06057727

Statistical Analysis Plan

01/07/2025

Objectives

Our primary objective is to test the effectiveness of multicomponent, personalized EHR-based nudges to both clinicians and patients for increasing flu vaccination completion among eligible primary care patients.

Relevant Study Design Details

Randomization

Primary care clinics will be randomized 2:1 to either a nudge intervention or usual care arm using covariate-constrained randomization, stratified by health system (Penn, UW). For the clinic level randomization, the covariate-constrained randomization will aim to balance the distribution of clinician panel baseline flu vaccination completion rate, panel size, and panel risk. Panel size is defined as the number of patient visits from September 1, 2022 through February 28, 2023. Panel risk is defined as the proportion of a clinician's patients who meet at least one of the following criteria: age \geq 70 years, Non-Hispanic Black race, residence in lower income communities (lowest quartile according to zip code), or no documented history of flu vaccine in the year prior. Second, patients who have an eligible appointment at an intervention clinic and are identified as high-risk for not completing a flu vaccination will be further randomized using a 1:1 ratio at the patient level—stratified by clinic—to receive either an additional, intensification nudge (bi-directional texting) or the standard nudge intervention (standard text messaging).

Blinding

All investigators, statisticians, and analysts will be blinded during the randomization, intervention, and analysis phases. They will be unblinded at the end of the study analyses, after all outcomes have been obtained.

Outcomes

The primary outcome is flu vaccination completion during the first eligible primary care visit.

Secondary outcomes are flu vaccination completion within 3 months of the first eligible primary care visit and flu vaccination ordering. These patient-level outcomes will be coded as a 1 to indicate completion (or signed order) and 0 to indicate non-completion (or unsigned/cancelled order).

Statistical Analysis

The primary analysis for all primary and secondary outcomes will follow the intent-to-treat principle.

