where A_1 is an indicator of whether the patient was seen at an active (1) or control (-1) clinic; A_2 is an indicator of intensive (1) or standard (-1) text messaging (patients who were actually randomized will have only one value for A_2 , while replicated patients will have one 1 and one -1); $A_1 A_2$ is the interaction between the patient’s cluster assignment and their individual-level assignment(s); and X is a vector of all other covariates we want to control for which will at minimum include mean-centered versions of the three variables used in the constrained randomization procedure: 1) clinic size (number of patient visits); 2) baseline clinic risk (proportion of panel deemed high risk); and 3) baseline clinic completion rate (proportion of panel with completed flu vaccination).

We will specify an independence working correlation when fitting the primary GEE model.

Although we expect some amount of correlation amongst observations within clinic, the replicated subject observations should be treated as independent. Fortunately, estimates from GEE models are robust to misspecification of the working correlation structure, meaning they are consistent for the true values even when the working correlation is specified incorrectly. Furthermore, when correlation amongst observations within clinic is low, the efficiency of using an exchangeable working correlation is similar to or worse than when using an independent working correlation. Since we will randomize 45 clinics, we will not use a small cluster correction.² We will use this approach for both the primary and secondary outcome analyses. Given model (1) with effect coding (i.e., -1 and 1 for levels of A_1 and A_2), we have the following:

1. The main effect of A_1 is $2\beta_1$ (i.e., the main effect of clinic-level nudges averaging over the differential effects of standard and intensive texting).
2. The main effect of A_2 given $A_1 = 1$ is $2\beta_2$. This is the comparison of text messaging intensity (standard versus intensive) given clinic-level nudges are active.
3. The comparison of clinic-level nudges with intensive texting versus control is $2\beta_1 + \beta_2$.
4. The comparison of clinic-level nudges with standard texting versus control is $2\beta_1 - \beta_2$.

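### Protocol and SAP disagree on whether baseline clinic flu vaccination rate is balanced and adjusted for, and the Lancaster replication is left on the protocol's two-variable rule

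*Protocol*

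**What the plan says.** **Protocol, randomisation (section 8.2).** For the main trial the procedure "stratifies by health system (Penn and UW) and balances the distribution of clinic size and panel risk across arms". For Lancaster the protocol states the rule again, "using the cvcrand package to balance the distribution of clinic size and panel risk across arms". The two-variable rule for the replication is therefore written down and does not arise from silence.

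**Protocol, model (section 9, Statistical Analysis).** The constrained randomisation is accounted for "by including health system, clinic size, and panel risk as covariates in the models for the effect of clinic-level nudges". Baseline vaccination rate is not in the list.

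**SAP, Randomization.** The constrained randomisation aims to "balance the distribution of clinician panel baseline flu vaccination completion rate, panel size, and panel risk".

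**SAP, covariates of model (1).** The minimum covariate set is the three variables said to have been used in the constrained randomisation: clinic size, baseline clinic risk and "baseline clinic completion rate (proportion of panel with completed flu vaccination"). This minimum list does not name health system, which the protocol's list does.

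**Scope.** The SAP describes clinics "stratified by health system (Penn, UW") and does not mention Lancaster anywhere. The protocol's Design section (5.1) says "We will use this design to replicate our findings at a third site, Lancaster General Health".

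**The concern.** Two documents describe one randomisation and one comparison with different covariate sets, and they cannot both be right about what was balanced at Penn and UW. This matters for the analysis because each document ties its adjustment set to the variables that were constrained.

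The second consequence concerns Lancaster. The SAP does not reach it, so the replication would follow the protocol: two balancing variables, and the same two in the model, since health system is constant within a single system. The trial being replicated would use three. For the clinic-level comparison nearly all the variance lies between clinics, so clinic-level predictors are the main route to a tighter estimate. A clinic's own earlier vaccination rate is a natural candidate, and the SAP authors chose it. Panel risk covers it only in part. It is the share of patients meeting any one of four criteria, and lack of a vaccine in the prior year is one of them alongside age, race and area income.

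**Working it through.** **Inputs from the documents.** ICC 0.02, average cluster size m = 1385, 48 clinics, target difference 7 points, stated power 85% (protocol section 9, Power Calculations); 2:1 allocation, so 32 nudge and 16 control clinics; two-sided alpha 0.025 (protocol and SAP). The SAP mentions 45 and 47 clinics in different places; 48 is used here because the stated power rests on it.

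**Assumptions.** The control-arm rate is not stated. Nor is r, the correlation between baseline and trial-season clinic rates net of the other covariates. Lancaster's clinic count is not given either (the protocol says only that it has more clinics and patients), so the 32:16 layout is a stand-in.

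**1. The plan's own figure.** Design effect = 1 + (1385 − 1) × 0.02 = 28.68. Effective control patients = 16 × 1385 / 28.68, with twice that in the nudge arm. Power for 7 points is 0.868 at a control rate of 30%, 0.846 at 35%, 0.832 at 40%, 0.826 at 46.5% and 0.858 at 60%. The stated 85% is thus reached for plausible control rates, with no term for baseline rate.

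**2. Share of variance between clinics.** The variance of a clinic's observed rate is proportional to ICC + (1 − ICC)/m = 0.02 + 0.98/1385 = 0.02071. The between-clinic share is 0.02/0.02071 = 97%.

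**3. Effect of adjusting on the standard error.** Adjustment reduces the between-clinic part to ICC × (1 − r²), so

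SE multiplier = √{[0.02(1 − r²) + 0.00071] / 0.02071}.

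**4. Effect on power at the stated 7-point target.** At 40% versus 47%, unadjusted SE = √[0.02071 × (0.40 × 0.60/16 + 0.47 × 0.53/32)] = 0.0217. Power = Φ(0.07/SE − 2.241), using unpooled variances. Unadjusted, 0.07/0.0217 = 3.22 and power is 0.837.

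| Assumed r | SE multiplier | Power |
|---|---|---|
| no adjustment | 1 | 84% |
| 0.1 | 0.995 | 84% |
| 0.3 | 0.96 | 87% |
| 0.5 | 0.87 | 93% |
| 0.7 | 0.73 | 99% |

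The SE multiplier hardly depends on the number of clinics, so it carries over to Lancaster better than the power column does.

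**5. Feasibility.** Protocol section 8.2 lists flu vaccination administration among the data extracted at all three systems, and prior-year vaccination is already needed to classify high-risk patients (inclusion criteria). The covariate can be computed without new data collection.

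**The case against.** The strongest reply is that balancing and adjusting on two prespecified covariates is a valid design, and a third is only an improvement in precision. That stands. Several stronger readings that a reader might infer are not supported.

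- *That Lancaster is certain to be randomised and analysed without baseline rate.* The replication is scheduled for year 3, and a separate Lancaster SAP may exist or follow. The documents show only that the text covering Lancaster omits the covariate.
- *That baseline rate is known to be a strong predictor.* No correlation is given. Panel risk already carries part of the signal. The predictor also differs from the outcome: the first is a panel-wide completion rate, while the second is vaccination at the first eligible visit among patients not yet vaccinated that season, with missed visits scored zero. A net r of 0.1 to 0.3 is plausible, and there the gain is small.
- *That chance imbalance in baseline rate is a separate hazard.* Unconstrained 32:16 allocation gives an SD of √[0.02 × 0.24 × (1/32 + 1/16)] = 2.1 points. Lancaster is, however, constrained on two variables, one of which overlaps with baseline rate. The figure is also essentially the between-clinic part of the 2.17-point SE above, so it is already in the power calculation.
- *That the replication is underpowered.* The documents name no target below 7 points and expect greater power at Lancaster.
- *That different adjustment makes the two odds ratios incomparable.* On the logit scale, ICC 0.02 corresponds to a between-clinic variance of about 0.02 × 3.29/0.98 = 0.067. Even at r = 0.8 the explained part is 0.64 × 0.067 = 0.043, and the usual attenuation approximation gives √(1 + 0.346 × 0.043) = 1.007, a shift of under 1% in the log odds ratio.

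None of this removes the disagreement between the two documents about Penn and UW.

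**Conclusion.** The inconsistency is established from the text and needs no assumption: the protocol uses two balancing variables, the SAP uses three, and the model covariates differ in the same way. Among the supplied documents Lancaster is governed by the two-variable rule, although the protocol says the same design is to be replicated there.

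The consequence is a loss of precision and some avoidable chance imbalance. Allocation remains random, so no bias follows, and the stated 85% power is neither wrong nor dependent on the covariate. The size of the loss turns on r: negligible at 0.1, modest at 0.3 and material from about 0.5. The power figures also rest on a 40% control rate and on the main trial's layout standing in for Lancaster's. The point is worth acting on because the correction costs almost nothing and the SAP has already adopted the covariate for the main trial.

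**What to change.** - Amend the Randomization text in protocol section 8.2 and the covariate paragraph in section 9 to add baseline clinic flu vaccination completion rate to both the balancing and the model covariates, naming Lancaster explicitly. Alternatively, extend the SAP to Lancaster.
- If Lancaster has already been randomised on two variables, leave the allocation as it is and add the baseline rate to its prespecified model before unblinding.
- Establish what was actually balanced at Penn and UW, and correct whichever document misstates it. State in the same edit whether health system belongs in the SAP's minimum covariate set.

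The cost is wording, one clinic-level variable from data already extracted, and one degree of freedom in the clinic-level model.

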We will test each of the four linear contrasts of the parameters estimated from the GEE model. We will use a Bonferroni correction for the first two contrasts, aligning with how the study was powered (i.e., two-sided significance level of 0.025 for the first two contrasts). We will consider contrasts 3 and 4 as exploratory, and thus we will not correct the corresponding p-values for multiple testing. Results will be reported on the odds ratio scale, including 95% confidence intervals. Confidence intervals for contrasts 1 and 2 will incorporate the Bonferroni correction used for the two tests.

Sensitivity Analyses to Evaluate Model Specifications

As a sensitivity analysis, we will restrict the data to high-risk patients at active clinics and estimate the main effect of intensive vs standard text messaging, specifying an exchangeable working

correlation within clinics. As another sensitivity analysis, we will use an exchangeable working correlation at the clinic level after duplicating each clinic's data, assigning one 1 and one -1 for patients without an individual-level assignment, and removing the record for each high-risk patient an intervention clinic corresponding to the opposite of the individual-level randomized assignment that was received. Duplicated clinics will be treated as independent while observations within clinic will be treated as exchangeable. In this way, duplicated records will be treated as independent. Using this approach, we will re-test the main effect of A_1 , i.e., $2\beta_1$, to evaluate sensitivity to specification of the working correlation. We will use a t-distribution with degrees of freedom equal to the number of clinics (47) minus the number of mean model parameters to construct a confidence interval for $2\beta_1$. If the interval does not include 0 (log odds ratio scale) we will reject the null and conclude there is a significant effect of clinic nudges compared to usual care.

Sensitivity Analyses to Evaluate Protocol Deviations

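### The protocol's power of at least 99% for comparison #2 does not follow from its stated inputs, which give about 91%

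*Protocol*

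**What the plan says.** The Power Calculations in Protocol section 9 cover two comparisons and state that "we used an adjusted Type I error of 0.025 to account for two comparisons". For comparison #2, the protocol says "we will have at least 99% power to detect a 2-percentage point difference" and adds that this holds "even if the rate of vaccination in the high-risk group is 50%, the most conservative rate with respect to power". On sample size it says: "This calculation assumed 1:1 individual-level randomization of n=1000 high-risk patients within each of N=32 clinics".

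The SAP (Analytical Plan for Primary and Secondary Outcomes) gives the sidedness, a "two-sided significance level of 0.025 for the first two contrasts", and says that this matches how the study was powered.

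Protocol section 9 (Statistical Analysis) plans robust standard errors without clustering for comparison #2, with clinic fixed effects. Patients who do not complete the visit are scored as not vaccinated. The stated inputs therefore call for neither a design effect nor a dropout allowance.

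**The concern.** Every quantity needed to reproduce the figure is stated, and the figure does not reproduce. Comparison #2 is one of only two comparisons with type I error control, and it serves the protocol's second objective, on disparities in high-risk subgroups. The power statement matters most if the result is null. At 99% power, a null result would be read as near-conclusive evidence against a 2-point effect; at 91% that reading is weaker. The protocol also uses these calculations as the benchmark when it expects greater power for both comparisons at the replication site.

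**Working it through.** **Inputs**

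| Input | Value | Source |
|---|---|---|
| High-risk patients randomised | 32 × 1,000 = 32,000 | Protocol section 9, Power Calculations |
| Per arm (1:1) | 16,000 | arithmetic |
| Rates | 50% v 52% | Protocol section 9 (50% rate, 2-point difference) |
| Alpha | 0.025, two-sided, z = 2.241 | Protocol section 9; SAP for sidedness |
| Design effect, dropout | none | Protocol section 9, Statistical Analysis |

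**Power at the stated inputs**

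- SE = √[(0.50 × 0.50 + 0.52 × 0.48) / 16,000] = 0.00559
- 0.02 / 0.00559 = 3.579
- 3.579 − 2.241 = 1.338
- Power = Φ(1.338) = 0.909

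The protocol's figure is at least 0.99.

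**Does another formula or reading give 99%?**

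| Variant | Power |
|---|---|
| Pooled variance; arcsine | 90.9% |
| Continuity correction | 90.8% |
| 48% v 50%, or 49% v 51% | 90.9% |
| Clinic strata removed (variance × 0.98, assuming the ICC of 0.02 stated for comparison #1) | 91.5% |
| One-sided 0.025 | 94.7% |
| One-sided 0.05 (contradicts the stated alpha) | 97.3% |
| All 1,385 patients per clinic treated as high-risk (22,160 per arm) | 97.6% |
| 1,000 per arm per clinic (32,000 per arm) | 99.8% |

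Only the last row exceeds 99%. It needs 2,000 high-risk patients per clinic, but the same paragraph gives an average of 1,385 patients of all risk levels. Using the total of 32,000 as the size of each arm would produce this result. That is a possible cause, but the documents do not show it.

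**What 99% power would need**

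- Sample size for 2 points: n per arm = (2.241 + 2.326)² × (0.2500 + 0.2496) / 0.02² ≈ 26,060. The total is about 52,120, and 52,120 / 32 ≈ 1,629 high-risk patients per clinic against the stated 1,000.
- Difference with 16,000 per arm: about 2.55 points.

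**Check of the method on comparison #1.** The design effect is 1 + (1,385 − 1) × 0.02 = 28.68. The effective sizes are 16 × 1,385 / 28.68 ≈ 773 (control) and 32 × 1,385 / 28.68 ≈ 1,545 (intervention). For a 7-point difference at two-sided 0.025, power is 87%, 83% and 83% at control rates of 30%, 40% and 50%. The control rates are my assumption, because the documents give none. The range brackets the stated 85%, so the same convention agrees with comparison #1 and the discrepancy is specific to comparison #2.

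**The case against.** The arithmetic is not in dispute. The objections concern its importance and scope.

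- **Little depends on the figure.** Enrolment is every eligible patient with a visit in the window, not a number derived from comparison #2. Comparison #1, at 85%, is the tighter calculation, and the SAP does not repeat the 99%. This stands, and it limits the consequence to the accuracy of the statement.
- **Actual numbers may be larger.** Protocol sections 5.6 and 5.7 plan 51,152 + 28,705 = 79,857 patients. Over 48 clinics that is about 1,664 per clinic, not 1,385. If the high-risk share stays at 1,000/1,385 (an assumption), there are about 1,201 high-risk patients per clinic, or about 19,220 per arm, and power is 95.4%. So 91% is a check of the stated inputs and not a forecast for the trial. This also stands, but 95.4% is still below 99%. Treating every patient in the intervention clinics (two-thirds of 79,857, or 26,619 per arm) as high-risk would give 99.1%, which departs from the stated inputs.
- **The SAP's test differs.** Its contrast 2 comes from a weighted and replicated model that includes low-risk patients, not from a simple comparison of two proportions. On the difference scale, the replicated low-risk rows shrink the effect and its standard error by the same factor, provided the standard error recognises that both copies are one patient. Power then stays near 91%. The objection does not restore 99%.

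**Conclusion.** The figure is wrong as written. On the protocol's own inputs (16,000 per arm, 50% v 52%, two-sided alpha 0.025), power is 90.9%, about 8 points below the stated minimum. The type II error is about 9% instead of at most 1%. No choice of formula or sidedness that keeps the stated alpha level, sample size, rate and difference exceeds about 95%.

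The conclusion rests on reading 1,000 as the high-risk patients per clinic across both arms, which is what the text says and the only reading compatible with 1,385 patients per clinic. Power of 91% is adequate, so the design stands and the stated figure needs correcting.

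**What to change.** Replace the sentence on comparison #2 in Protocol section 9 with one of these:

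- about 91% power for a 2-point difference at a 50% rate (16,000 per arm, two-sided alpha 0.025);
- 99% power for a difference of about 2.6 points on the same inputs; or
- the 99% figure together with the inputs that produce it.

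If the figure is updated for the clinics actually randomised, first reconcile their number. The protocol assumes 48. The SAP gives 45 in one place ("Since we will randomize 45 clinics, we will not use a small cluster correction") and 47 in another ("degrees of freedom equal to the number of clinics (47) minus the number of mean model parameters"). Keeping 1,000 high-risk patients per clinic as an assumption, 30 intervention clinics (two-thirds of 45) give about 89% and 31 (about two-thirds of 47) give 90.0%.

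The cost is one sentence and a less favourable figure. No extra patients and no change to the analysis are needed.
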